### **Asymptomatic hypoglycemia**

Asymptomatic hypoglycemia is an event not accompanied by typical symptoms of hypoglycemia but with a measured plasma glucose concentration  $\leq 70$  mg/dL ( $\leq 3.9$  mmol/L).

**Note:** Low plasma glucose values without symptoms or signs should not be reported more than once within 30 minutes. Repeated low glucose values within a short period could be due to malfunction of the device, error testing, or following up a low glucose reading. The Investigator should try not to document false low SMBG values or redundant low glucose values as asymptomatic hypoglycemic events. Further clarification with the patients is needed.

### **Probable symptomatic hypoglycemia**

Probable symptomatic hypoglycemia is an event during which symptoms of hypoglycemia are not accompanied by a plasma glucose determination, (but that was presumably caused by a plasma glucose concentration  $\leq 70$  mg/dL [ $\leq 3.9$  mmol/L]), ie, symptoms treated with oral carbohydrate **without** a test of plasma glucose.

### **Relative hypoglycemia**

Relative hypoglycemia, recently termed “pseudo-hypoglycemia” (21), is an event during which the patient reports typical symptoms of hypoglycemia, and interprets the symptoms as indicative of hypoglycemia, but with a measured plasma glucose concentration  $> 70$  mg/dL ( $> 3.9$  mmol/L).

## **10.7 ADVERSE EVENTS MONITORING**

All events will be managed and reported in compliance with all applicable regulations, and included in the final CSR.

## 11 STATISTICAL CONSIDERATIONS

### 11.1 DETERMINATION OF SAMPLE SIZE

The sample size/power calculations were performed based on the primary variable of change from Baseline to Week 26 in HbA1c (%).

Assuming a common standard deviation (SD) of 1.2% and using a 2-sided test at a 0.05  $\alpha$ -level, 360 patients (120 patients per arm) will have 97% power to detect a treatment difference of -0.6% in mean HbA1c change from Baseline to Week 26 between sotagliflozin 400 mg and placebo.

This sample size will also allow to exclude a decline in BMD from Baseline of >2% with a 95% power, assuming a missing rate of 30% and an SD of 3.5%.

The total sample size will be approximately 360 patients to be randomized (120 in sotagliflozin 200 mg group, 120 in sotagliflozin 400 group, and 120 in placebo group).

Calculations were made using East 6.4 software.

### 11.2 DISPOSITION OF PATIENTS

The total number of patients for each of the following categories will be presented in the CSR:

- Screened patients: patients who have signed the ICF.
- Run-in patients.
- Randomized patients: patients with a treatment kit number allocated at randomization and recorded in IRT database, regardless of whether the treatment kit was used or not.
- The safety population (ie, randomized and treated patients).
- The Intention-to-Treat (ITT) population, as defined in [Section 11.3.1.1](#).
- The randomization strata (HbA1c at Screening [ $\leq 8.5\%$ ,  $>8.5\%$ ]) and sex (female, male). Any discrepancy between the strata assigned by IRT and the information reported on eCRF will be listed for all randomized patients.
- Patients who have completed the 26-week Double-blind Core Treatment Period.
- Patients who discontinued the IMP during the 26-week Double-blind Core Treatment Period, and the reasons for treatment discontinuation.
- Patients who have completed the 104-week Double-blind Treatment Period.
- Patients who discontinued the IMP during the 104-week entire double-blind treatment period, and the reasons for treatment discontinuation.
- Patients who have completed the study.
- Patients who discontinued the study, and the reasons for study discontinuation.

For all categories of patients except screened, percentages will be calculated using the number of randomized patients as denominator for each treatment group.

A listing of patients prematurely discontinued from the treatment, along with reasons for discontinuation, will be provided. Similarly, a listing of patients prematurely discontinued from the study, along with reasons for discontinuation, will be provided.

Patients treated without being randomized will not be considered as randomized and will not be included in any efficacy population. The safety experience of patients treated and not randomized will be reported separately, and these patients will not be included in the safety population.

Patients randomized but not treated and patients randomized but not treated as randomized will be identified and described in separate listings.

For any patient randomized more than once, only the data associated with the first randomization will be used in any analysis population. The safety experience associated with any later randomization will be assessed separately.

### **11.3 ANALYSIS POPULATIONS**

#### **11.3.1 Efficacy population**

Efficacy analyses will be based on the treatment group allocated by the IRT according to the randomization schedule at randomization visit (as randomized), irrespective of the treatment actually received.

##### ***11.3.1.1 Intent-to-treat population***

Efficacy analyses will be based on the ITT population, defined as all randomized patients, irrespective of compliance with the study protocol and procedures. Patients will be analyzed for efficacy analyses according to the treatment group to which they are randomized.

#### **11.3.2 Safety population**

The safety analysis will be conducted on the safety population, defined as all randomized patients who did actually receive at least one dose of study treatment during the treatment period (regardless of the amount of treatment administered). Patients will be analyzed according to the treatment actually received.

In addition:

- Nonrandomized but treated patients will not be part of the safety population, but their safety data will be presented separately.
- Randomized patients for whom it is unclear whether they took the study medication will be included in the safety population as randomized.

- When a patient is exposed to both sotagliflozin and placebo, the patient will be analyzed in the sotagliflozin group (depending on the treatment kit taken [400 mg or 200 mg]).
- When a patient is exposed to both sotagliflozin 400 mg and sotagliflozin 200 mg, the patient will be analyzed in the sotagliflozin 200 mg group.
- Randomized patients will be excluded from the safety population only if there is documented evidence (ie, all study dates recorded as no medication taken) that patients have not taken the study medication.

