2.2.1 Randomization and drug dispensing irregularities

Randomization and drug-dispensing irregularities occur whenever:

1. A randomization is not in accordance with the protocol-defined randomization method, such as a) an ineligible patient is randomized, b) a patient is randomized based on an incorrect stratum, c) a patient is randomized twice, or d) in a dynamic randomization scheme the treatment assignment is, in fact, not random, due to a computer program error.

OR

2. A patient is dispensed an IMP kit not allocated by the protocol-defined randomization, such as a) a patient at any time in the study is dispensed a different treatment kit than as randomized (which may or may not contain the correct-as-randomized IMP), or b) a nonrandomized patient is treated with IMP reserved for randomized patients.

Randomization and drug-dispensing irregularities will be monitored throughout the study and reviewed on an ongoing basis.

All randomization and drug-dispensing irregularities will be documented in the clinical study report. If the number of irregularities is large enough to make a tabular summary useful, the irregularities will be categorized and summarized among randomized patients (number and percentages). Nonrandomized, treated patients will be described separately. Listings with additional, relevant details will be provided in appendix.

Randomization and drug-dispensing irregularities to be prospectively identified include but are not limited to:

Randomization and drug allocation irregularities

Kit dispensation without IRT transaction

Erroneous kit dispensation

Kit not available

Randomization by error

Patient randomized twice

Stratification error

Patient switched to another site

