2.3.2 Safety population

Safety analyses will be based on the safety population, defined as all randomized patients who actually receive at least one dose of double-blind IMP (regardless of the amount of treatment administered). Patients will be analyzed according to the treatment actually received.

In addition:

- Nonrandomized but treated patients will not be part of the safety population; however, their safety data will be presented separately.
- Randomized patients for whom it is unclear whether they took the IMP will be included in the safety population as randomized.
- When a patient is exposed to both sotagliflozin and placebo, the patient will be analyzed in the appropriate sotagliflozin group (depending on the treatment kits taken [400 mg or 200 mg]).
- When a patient is exposed to both sotagliflozin 400 mg (treatment kits) and 200 mg (treatment kits), the patient will be analyzed in the sotagliflozin 200 mg group.
- Randomized patients will be excluded from the safety population only if there is documented evidence (ie, all study dates recorded as no medication taken) that patients have not taken the study treatment. If a patient is dispensed double-blind IMP and is lost to follow-up without any documented evidence, the patient will be considered exposed.

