2.4.5 Analyses of safety data

The summary of safety results will be presented by treatment group. The safety data will be summarized for the 26-week core treatment period and the 104-week entire treatment period separately, unless otherwise specified.

The observation period defined in [Section 2.1.4](#) is applicable in all safety analyses for classification of AEs, determination of treatment-emergent Potentially Clinically Significant Abnormality (PCSA) values and the last on-treatment value for laboratory, vital sign, BMD and ECG.

General common rules

All safety analyses will be performed on the safety population as defined in [Section 2.3.2](#), unless otherwise specified, using the following common rules:

- Safety data in patients who do not belong to the safety population (eg, exposed but not randomized) will be listed separately.

- The baseline value (with the exception of serum creatinine and eGFR) is defined as last available value before the first dose of double-blind IMP. For creatinine and eGFR, the baseline value is defined as the average of all values before the first dose of double-blind IMP.
- PCSA values are defined as abnormal values considered medically important by the Sponsor according to predefined criteria/thresholds based on literature review and defined by the Sponsor for clinical laboratory tests, vital signs, and ECG (Appendix A).
- PCSA criteria will determine which patients had at least one PCSA during the TEAE period, taking into account all evaluations performed during the TEAE period, including nonscheduled or repeated evaluations, central laboratory/reading or local measurements (see [Section 2.5.4](#)). The number of all such patients will be the numerator for the on-treatment PCSA percentage.
- The treatment-emergent PCSA denominator by group for a given parameter will be based on the number of patients assessed for that given parameter in TEAE period by treatment group on the safety population.
- For laboratory parameters cited in the protocol as efficacy endpoints (eg, HbA1c, plasma glucose, etc.), PCSA summaries will not be provided. These parameters will be summarized in efficacy [Section 2.4.4](#).

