2.4.5.1 Analyses of the Bone Mineral Density

Analysis of percent change from Baseline in BMD (lumbar spine, total hip, femoral neck) to Week 26, Week 52, and Week 104 will be performed on the safety population, using BMD measurements obtained during the study, regardless of IMP discontinuation and/or introduction of rescue therapy. No statistical significance tests will be performed.

All planned analyses will be performed at each location (lumbar spine, total hip, and femoral neck) separately.

Analysis of the key secondary safety endpoints of percent change from Baseline to Week 26, Week 52, and Week 104 respectively in BMD will be performed by an ANCOVA model using BMD values measured at Baseline and the corresponding time point (observed or imputed). The missing data at endpoint will be imputed by multiple imputation (MI) methods as detailed below.

Missing endpoint data at Week 26, Week 52, or Week 104 will be imputed using a model built separately in each treatment group and estimated from the patients in the same treatment group who prematurely discontinue the IMP before the endpoint (Week 26, Week 52, or Week 104) but have the measurement for the endpoint (retrieved dropouts). The imputation model will include the randomization strata and the baseline value. In cases of non-convergence during the imputations, the offending stratum will be identified and then will be dropped from the model. Considering that the number of retrieved dropout patients in each treatment group is expected to be small, a simple imputation model based on regression will be used with baseline measurement included as the predictor. This will serve as the primary method of imputation for missing data should sampling criteria be satisfied (ie, ≥ 5 retrieved dropouts in each treatment group).

In addition, a sensitivity analysis using a pattern-based multiple imputation method will be performed. The imputation method will be implemented in 3 steps:

1. For missing data at Baseline, a monotone missingness method implemented in PROC MI with monotone regression option will be used to impute the missing data at Baseline. The imputation model will include the randomization strata and BMD measurements at Baseline.

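### Any exposure to both doses places a patient in the 200 mg safety group, with no minimum, so 400 mg data can be filed under 200 mg but never the reverse

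*Protocol*

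**What the plan says.** The two documents agree. Protocol 11.3.2 gives the rule for mixed dosing as "exposed to both sotagliflozin 400 mg and sotagliflozin 200 mg, the patient will be analyzed in the sotagliflozin 200 mg group". SAP 2.3.2 words it by kit: "exposed to both sotagliflozin 400 mg (treatment kits) and 200 mg (treatment kits), the patient will be analyzed in the sotagliflozin 200 mg group". Neither names a number of doses, a number of days or a predominant-dose criterion.

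The rule reaches widely. SAP 2.4.5 states: "All safety analyses will be performed on the safety population as defined in" Section 2.3.2, unless otherwise specified. For BMD, SAP 2.4.5.1 says that the analyses at "Week 26, Week 52, and Week 104 will be performed on the safety population, using BMD measurements obtained during the study". SAP 2.4.3 summarizes exposure by actual treatment in the same population, and SAP 2.4.5.3 does the same for events of special interest, which include adjudicated fractures. Only efficacy is grouped as randomized (Protocol 11.3.1, SAP 2.3.1).

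The trigger is foreseen. SAP 2.2.1 counts as an irregularity that "a patient at any time in the study is dispensed a different treatment kit than as randomized", and notes that such a kit may still hold the right product. SAP 2.2 lists patients whose treatment differed from their randomization, and SAP 2.4.3.1 tabulates final dose by group. I found no as-randomized or predominant-dose sensitivity analysis for safety.

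**The concern.** The rule has no threshold and it is asymmetric. A patient randomized to 400 mg who takes that dose for nearly 104 weeks and takes one dose from a 200 mg kit is a 200 mg patient in every safety table. A patient randomized to 200 mg who takes a 400 mg kit also counts as 200 mg. In both cases, exposure and events that arose on 400 mg are shown under 200 mg.

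Protocol 4.3 says the study should characterize the bone safety of both doses and the effect of each. A grouping that can take patients and events out of the higher dose, and never add them, works against that aim. 400 mg is also the dose in the primary objective. What is at stake is the descriptive attribution of uncommon events to dose, and a slight blurring of the contrast between the two doses.

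**Working it through.** **When the rule applies.** The kit must be a 200 mg kit from which at least one dose was taken. A misdispensed kit that holds 400 mg changes nothing. A placebo kit leaves the patient in the sotagliflozin group. Because the SAP rule is by kit, a 400 mg patient who takes one tablet too few is not moved.

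**Inputs from the documents.** 120 patients per arm; BMD SD 3.5%, 30% missing, 2% margin, 95% power (Protocol 11.1). Double-blind product is dispensed at Visits 3 to 12, which is 10 dispensings, of which Visits 3 to 7 (5) precede the Week 26 visit (Protocol 1.2). Treatment lasts 728 days.

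**Assumed, because not given.** The cross-dose kit error per dispensing (e = 0.1% to 0.5%), the BMD difference between doses, and the number of fractures.

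**The plan's BMD figure.** Evaluable patients per arm: 120 × 0.70 = 84. SE of a between-arm difference: 3.5 × √(2/84) = 0.54 percentage points. Power to exclude 2% when the true difference is 0, two-sided 0.05: Φ(2/0.540 − 1.96) = Φ(1.74) = 0.959. The stated 95% reproduces, so 0.54 is a fair yardstick.

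**Patients moved.** Proportion = 1 − (1 − e)^k for k dispensings, times 120.
- k = 10: 1.0% (e = 0.1%) to 4.9% (e = 0.5%), or 1.2 to 5.9 patients.
- k = 5: 0.5% to 2.5%, or 0.6 to 3.0 patients.

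**Exposure.** One fully treated patient carries 728/365.25 = 2.0 of the arm's 120 × 728/365.25 = 239.2 patient-years.

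**Mean BMD.**
- The 200 mg mean shifts by m/(120 + m) × d for m moved patients and a dose difference d. With m = 4 and d = 0.6 points: 4/124 × 0.6 = 0.019.
- With d = 0.3 points, the gap between the two canagliflozin doses cited in Protocol 4.4 (−0.9% and −1.2%), and m = 6: 6/126 × 0.3 = 0.014.
- Removing one 400 mg patient with a 7% loss shifts that arm's mean by (arm mean + 7)/(n − 1). With arm mean 0 and n = 84: 7/83 = 0.084. With arm mean −2 and n = 120: 5/119 = 0.042.

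All are small against 0.54.

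**A rare event.** Suppose 4/120 (3.3%) fracture on 400 mg and 3/120 (2.5%) on 200 mg. Moving one patient with a fracture gives 3/119 (2.5%) and 4/121 (3.3%). How likely that is depends on the moved patient being one with a fracture: 1.2 × 4/120 = 0.04 to 5.9 × 4/120 = 0.20 such patients expected.

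**The case against.** The strongest case for leaving the rule alone has five parts.

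- It is prespecified, identical in both documents and blind to outcome. For 200 mg against placebo it is cautious, because it never removes an event from the lower dose. This stands; the concern is for 400 mg only.
- If kit errors are unrelated to outcome, the 400 mg event rate is unbiased on average, because the denominator falls as well. Moving a patient without an event even raises it slightly (4/119 = 3.36% against 4/120 = 3.33%). This stands too. The rule is anti-conservative in that 400 mg event counts can only stay or fall, and in that the 200 mg group is pulled toward 400 mg.
- The error rate is assumed, and kits are allocated centrally by number through the IRT. The number affected may be zero.
- Such patients are already visible in the listings, the irregularity reporting and the final-dose table. That is true, but none of these changes the group used in any estimate.
- A longest-duration rule has a mirror fault: an event during the shorter exposure is shown under the other dose. This also stands, but it applies in both directions and involves the smaller share of the patient's exposure.

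**Conclusion.** The point holds as a low-severity improvement. The rule, its scope and its one-way direction are plain in the text. Its practical size is unknown and probably small: about 1 to 6 of 120 patients over the study under the assumed error rates, a mean BMD shift of about 0.02 to 0.08 points, and a possible change of one in a rare-event count. The BMD arithmetic treats values as observed. SAP 2.4.5.1 imputes by group from retrieved dropouts and requires at least 5 in each group, so a moved patient who is one of those would carry more weight than shown.

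Three stronger readings are tempting, and the documents do not support them.

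- A reader might infer that the rule destroys the randomized BMD comparison. The shift is small against the SE of 0.54, and BMD carries no significance test.
- A reader might infer that it could settle the fracture result or reverse a dose relation. In the example, both splits are compatible with no difference (Fisher p = 1.0). The planned BMD contrasts are each dose against placebo, other safety analysis is essentially descriptive, and I found no planned 400 versus 200 mg test.
- A reader might infer that a 200 mg kit taken at Week 86 would overturn the Week 26 BMD result already submitted. The protocol summary counts that analysis among the final ones at the first step, SAP Section 3 also places it there, and no section says it is rerun under new groups. At most, a repeated by-visit summary could show a slightly different Week 26 row.

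**What to change.** In Protocol 11.3.2 and SAP 2.3.2, assign a patient exposed to both doses to the dose taken for the longest duration, and to the randomized dose if the durations are equal. In SAP 2.4.5.1, and in Protocol 11.4.3.1 to match, run the BMD ANCOVA in treated patients as randomized. Week 26 grouping for that analysis then cannot change with later kits, and no separate freeze of assignments at the first-step lock is needed. Report the number of patients with mixed exposure by randomized group.

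The cost is a short text change in each document, with the protocol part going through the amendment process in Section 15, and one derived variable. No new data are needed. There are two small downsides. An event during the shorter exposure appears under the predominant dose, which the planned listing of patients whose treatment differed from randomization makes visible. The BMD ANCOVA would also be grouped differently from the other safety tables, so its table titles should say so.

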## 11.4 STATISTICAL METHODS

Continuous data will be summarized by treatment group using the number of observations available (N), mean, SD, minimum, median, and maximum.

Categorical data will be summarized by treatment group using count and percentage.

In general, descriptive statistics of quantitative efficacy and safety parameters (result and change from Baseline) by scheduled visits will be provided on observed cases (OC), ie, inclusion of only patients having nonmissing assessments at a specific visit.

The Baseline value is defined generally as the last available value before the first dose of double-blind IMP or the last available value prior to randomization for patients who were randomized but never exposed to IMP.

For serum creatinine and eGFR, the Baseline value is defined as average of all values before the first dose of double-blind IMP for those randomized and exposed or before randomization for patients who were randomized but never exposed to IMP.

Analysis of demographics and Baseline characteristics and prior and concomitant medications will be provided in detail in the Statistical Analysis Plan (SAP).

### 11.4.1 Extent of study treatment exposure and compliance

The extent of study treatment exposure and compliance will be assessed and summarized by actual treatment received within the safety population.

#### 11.4.1.1 Extent of investigational medicinal product exposure

The extent of study treatment exposure will be assessed by the duration of treatment exposure during the study.

The duration of treatment exposure will be the total number of days of administration of the double-blind IMP, regardless of unplanned intermittent discontinuations. The duration of IMP exposure will be calculated as:

$$(\text{Date of the last double-blind IMP taken} - \text{Date of the first double-blind IMP taken}) + 1$$

The number (%) of patients randomized and exposed to double-blind IMP will be presented by specific time periods for each treatment group. The time periods of interest will be defined in the SAP.

Descriptive statistics of duration of treatment exposure (number, mean, SD, minimum, median, and maximum) and cumulative exposure in patient year will also be presented by treatment group in the safety population.

